## **BACKGROUND AND SIGNIFICANCE**

Provide a brief paragraph summarizing prior experience important for understanding the proposed study and procedures.

*Cannabis sativa* has been used medicinally for a range of disorders for thousands of years, including anxiety. Cannabis is comprised of more than 100 cannabinoids; D-tetrahydrocannabinol (Δ9-THC) is the major psychoactive constituent, and cannabidiol (CBD) is the major non-psychoactive constituent that has been touted to have a variety of potential medicinal benefits. Industrial hemp is a variety of the *Cannabis sativa* plant, which until recently was grown specifically for industrial uses, such as textiles. Hemp has much lower concentrations of THC than cannabis, defined as THC<0.3% by weight. In recent years, some hemp strains have been bred to produce particularly high concentrations of CBD with very low concentrations of THC, virtually eliminating the potential for intoxicating effects. Extracts from these hemp strains are manufactured into a variety of oils, capsules, sprays, etc., available in brick-and-mortar stores across the country as well as on the Internet.

Previous studies have demonstrated CBD's acute anxiolytic potential in both animals and humans. Recently, our group began the first ever clinical trial of a high-CBD compound for anxiety. This trial, studied under IND [REDACTED], examines the impact of a high-CBD, low-THC cannabis-derived sublingual solution on measures of anxiety, mood, quality of life, and cognition over a 4-week treatment period. Interim analyses completed on the first 5 subjects who completed the trial were extremely compelling; analyses indicate that patients reported a 68.29% reduction in anxiety symptoms on the primary outcome measure, the Beck Anxiety Inventory (BAI), from the baseline to final visit. The study product is very well-tolerated, with no serious adverse events occurring to date.

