In order to assess the efficacy of the dose chosen for the double-blind study, we will also conduct a small open-label trial of the CBD solution prior to initiating the double-blind study. This open-label trial will enroll up to 12 participants who are interested in using CBD, and who have anxiety. This trial will determine whether patients derive clinical benefits at the current dosage proposed for the active treatment arm of the double-blind trial. This trial will examine all components of the originally proposed study.

Subjects will be recruited through IRB-approved advertisements and flyers in regions that have approved medical marijuana. Additionally, medical marijuana healthcare facilities throughout New England, including CannaCare, Integr8, MMJ Physician Practice, and others, may also refer interested patients to contact the study recruitment line for further screening. These healthcare groups provide their interested patients who meet for general inclusion criteria with study recruitment materials. The total sample size for the double-blind study is 40 (20 CBD, and 20 placebo); up to 15 of each group (30 total) will also complete the MRI scanning protocol. For the open-label trial, the total sample size is 12.

Inclusion Criteria:

- 1) Subject has provided informed consent
- 2) Subject is 18 or older
- 3) Subject is a native English speaker or acquired English prior to age 5
- 4) Subject scores a minimum of 16 on the Beck Anxiety Inventory (BAI) OR a minimum of 8 on the Overall Anxiety Severity and Impairment Scale (OASIS) at the screening visit

Exclusion Criteria:

Subjects will be excluded if they report any of the following:

- 1) Non-native English speakers
- 2) Estimated IQ < 75
- 3) Meets criteria for DSM-IV classification of current substance abuse/dependence, psychotic disorder, bipolar disorder, or an eating disorder
- 4) A first-degree relative with a psychotic disorder
- 5) A history of head injury or loss of consciousness greater than 5 minutes
- 6) Currently uses marijuana or cannabinoid-based products more frequently than 1x/month
- 7) Female subjects will be excluded if they have a positive urine pregnancy test, or if they are currently breastfeeding
- 8) Presence of a serious medical illness, including liver, kidney, or cardiovascular disease, or neurological disorder
- 9) Allergy to coconut oil

- 10) Current use of valproate
- 11) Currently enrolled in other research studies or clinical trials involving interventions

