### **Double-Blind Trial**

Individuals will be assessed in-person at baseline and weekly for 6 weeks of treatment with compounds administered as sublingual solutions in a double-blind, randomized procedure: subjects will receive either the CW solution or matched placebo. At the weekly visits throughout the treatment period, individuals will complete clinical scales and have a check-in with study staff.

In addition to clinical ratings and a check-in with study staff, neuropsychological testing will be performed at baseline and week 6 in order to assess cognitive performance. Finally, a subset of individuals will receive an hour-long MRI scan at baseline and week 6, with both resting state and task-related functional magnetic resonance imaging (fMRI) in each MRI session. In addition, a brief diffusion tensor imaging (DTI) sequence will also be acquired to examine white matter fiber tract integrity, and magnetic resonance spectroscopy (MRS) will be conducted to examine levels of certain metabolites in the brain. Subjects will also provide a buccal swab sample for genetic analysis at the baseline visit.

[figure not shown]
At the end of the baseline visit, eligible subjects will be randomized to either CW solution or placebo using a standard alternating procedure in accordance with the McLean Pharmacy. Subjects will be instructed on how to administer the compound, as described above.

For both the open-label and double-blind trials, the baseline and the final study visits are estimated to take approximately 3-4 hours, with the weekly visits in the interim estimated to take approximately 1 hour, and 15 minutes for phone check-ins, for a total of approximately 10-12 hours required to complete all possible visits. Urine samples will be collected at every other visit (Visits 1, 3, 5, and 7) to measure THC via GCMS (Quest Diagnostics) and to monitor for the presence of other substances throughout the study. Female subjects will be informed that their sample will also be used to confirm negative pregnancy (HCG) status; if at any point their urine tests positive for HCG, they will be excluded from the study. We are currently in communication with several groups that may be able to assess for CBD in urine; we hope to utilize one of these groups to quantify CBD in urine throughout the study.

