#### Clinical Ratings

The Structured Clinical Interview for DSM-V Patient Version (SCID-P) and the SCID-P Substance Abuse/Dependence Module or the Quick Structured Clinical Interview for DSM-V Disorders (QuickSCID) will be administered to all study participants during visit 1 by the Principal Investigator, a Clinical Neuropsychologist or trained Clinical Research Assistant. Subjects will also complete clinical rating scales and questionnaires that have been shown to provide reliable estimates of current clinical state and are easily administered. They will also complete quality of life measures. All subjects will be given the following measures at the baseline and final visits that take approximately one hour to complete:

Subjects will also complete a subset of these measures, specifically the anxiety and mood-related measures [REDACTED], along with the SEQ, at each weekly visit. An Abuse Liability Rating Scale (ALR) will be completed at V3 and V7.

Please note that if suicidality is endorsed spontaneously, on any of the clinical scales, or during the SCID or weekly check-ins with study staff, the patient will be immediately assessed for suicidality risk. Please see “Suicidality SOP” attachment for further information.

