#### Neuropsychological Assessment

In addition to the clinical rating scales, the proposed investigation also includes a brief battery of neuropsychological tests to examine the potential effects of CBD on cognition in subjects with anxiety. Individuals will complete neuropsychological assessments at two time points; at baseline and after 6 weeks of treatment. The neurocognitive battery is primarily designed to evaluate frontal, executive, and memory functions as well as general intellectual capacity. The neuropsychological measures will be administered by a trained psychometrician and were chosen because they are standard, well-known measures that can be administered and scored reliably. Measures to be administered at baseline and both follow-up visits include the [REDACTED]

[REDACTED]. The neurocognitive assessment battery will take approximately 1.5 hours to complete. Many of these tests, including the [REDACTED] [REDACTED] have alternate versions to use at the follow-up visit, in order to reduce the likelihood that subjects remember portions of the assessments from baseline.

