#### **STATISTICAL APPROACHES**

All statistical analyses will be conducted using IBM SPSS Statistics (version 28). Data will be screened for outliers and any data points more than 2 standard deviations from the group means will be excluded. Additionally, data will be screened for skew, kurtosis, non-normality, and homogeneity of variance. If the assumptions of parametric inferential analyses are not met, the appropriate non-parametric analyses (e.g. Wilcoxon-Signed Rank Test) will be performed. Descriptive statistics will be used to characterize the demographic data. Baseline clinical and neuropsychological data will be assessed using 2-tailed paired *t*-tests to compare follow-up timepoints to baseline values. When needed, Bonferroni corrections for multiple comparisons will be utilized.

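### Bonferroni is promised only when needed, with no trigger, family or alpha and no primary scale or week, so familywise error control is not guaranteed

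*Combined protocol and SAP*

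**What the plan says.** The rule is one sentence in Statistical Approaches: "When needed, Bonferroni corrections for multiple comparisons will be utilized". The tests it governs come just before it: "Baseline clinical and neuropsychological data will be assessed using 2-tailed paired" t-tests, used "to compare follow-up timepoints to baseline values". The section states no significance level and ranks no scale or visit.

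The number of tests follows from the visit schedule:

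- **Visits.** Under Double-Blind Trial: "Individuals will be assessed in-person at baseline and weekly for 6 weeks of treatment". That gives six follow-up timepoints.
- **Weekly scales.** Under Clinical Ratings, for each weekly visit: "Subjects will also complete a subset of these measures, specifically the anxiety and mood-related measures". The names and number are redacted, but the wording is plural.
- **Cognition.** Under Neuropsychological Assessment: "Individuals will complete neuropsychological assessments at two time points; at baseline and after 6 weeks of treatment". That gives one comparison per measure.
- **Sample size.** Under Research Design and Methods: "The total sample size for the double-blind study is 40 (20 CBD, and 20 placebo").

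The visible text calls the BAI primary only in Background and Significance, where it reports a "reduction in anxiety symptoms on the primary outcome measure, the Beck Anxiety Inventory (BAI), from the baseline to final visit". That passage concerns the investigators' other trial, of a cannabis-derived product. In this trial the BAI appears as an entry criterion and as the scale that defines clinical improvement in the open-label phase. It is not labelled as the primary endpoint of the double-blind phase.

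**The concern.** A multiplicity rule works only if a reader can tell beforehand which p-values it covers and by how much each is adjusted. This one leaves both open. Two analysts could follow it faithfully, one dividing alpha by the number of weeks on each scale and the other judging correction unnecessary for the main anxiety scale, and reach different significance conclusions from the same data.

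With no primary scale or week, there is also no single test that could stand uncorrected at the full level. A positive result at one week on one scale would be hard to interpret, because the reader could not tell how many chances it had.

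**Working it through.** The plan states no alpha, familywise rate or power, so there is no figure of its own to reproduce. The check asks what the error rate is if the correction is never used, and what it is if the correction is always used.

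**Inputs.** Six follow-ups, two-sided paired t-tests and n=20 per arm come from the plan. Alpha 0.05 per test, no true mean change, and the correlations below are assumptions.

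**1. Independent tests, one scale, six weeks (upper-end reference).**
1 - (1 - 0.05)^6 = 1 - 0.735 = 26.5%.

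**2. Correlated tests, one scale, six weeks.** All six changes share one baseline. If raw scores have common variance s² and equal correlation r between visits, each change has variance 2s²(1 - r). Two changes then have covariance s²(r - r - r + 1) = s²(1 - r). Their correlation is (1 - r)/(2(1 - r)) = 0.5, whatever r is. The correlation that drives the error rate is therefore that among change scores, and it must be labelled as such. Simulation with n=20 (100,000 runs per row):

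| Correlation assumed | Chance of at least one p<0.05 |
|---|---|
| Raw scores 0.5, 0.6 or 0.8, equal, shared baseline | about 21% |
| Change scores 0.5 | 21% |
| Change scores 0.6 | 19% |
| Change scores 0.7 | 17% |
| Change scores 0.8 | 14.5% |
| Change scores 0.9 (very favourable) | 11% |

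Over change-score correlations of 0.5 to 0.8 the range is about 15-21%, roughly three to four times 5%.

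**3. More than one weekly scale.** The number is redacted, so this is illustration only. With two scales, raw-score correlation 0.5 over time and 0.3 to 0.8 between scales, the simulated rate at n=20 is 31-37%. It rises further with each added scale.

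**4. Correction always applied.** With one scale over six weeks the per-test level is 0.05/6 = 0.00833.

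- Independent tests: 1 - (1 - 0.00833)^6 = 4.9%.
- Change-score correlations 0.5 to 0.8 (simulated): 4.2% down to 3.0%.

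A defined Bonferroni family would therefore keep the rate at or below 5%.

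**5. One prespecified test.** With one primary scale at one week, m = 1 and the rate is 5% with no correction.

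**The case against.** The strongest reply is that the plan does promise correction. Six tests of one scale are the ordinary case for needing it, and a team that applied Bonferroni to the full family would keep the error at or below 5%. This stands: the 15-21% is the rate with no correction at all, not a forecast of what the team will do. What remains is that the wording permits anything between the two and commits to neither.

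A second reply is that the null in the calculation is no change from baseline. Entry requires a raised BAI or Overall Anxiety Severity and Impairment Scale (OASIS) score, so regression to the mean can produce change with no drug effect. This also stands. The figures are error rates for within-group change. Correcting the paired tests would not turn them into a CBD-versus-placebo comparison.

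A third reply is that a primary label could sit in the redacted measures list. That is possible, and the redaction is not a fault. It would still leave unstated when and over what Bonferroni applies.

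Four stronger readings are tempting, and the documents do not support them:

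- **That any week on any scale may be declared positive under the plan as written.** The plan says Bonferroni will be used when needed, so this is the worst case and not the rule.
- **That the need for correction is judged after the data are seen.** The section does not say when it is judged.
- **That dozens of tests are planned, imaging included.** The paired-test sentence covers clinical and neuropsychological data only, cognition adds one comparison per measure, only a subset of the clinical scales is weekly, and the counts are redacted.
- **That Bonferroni over everything would remove most of the power.** This depends on the effect size, which the plan does not give. For a paired test at n=20 and 24 tests (four scales by six weeks, assumed), power falls from 92% to 52% at a standardized change of 0.8 and from 99% to 80% at 1.0. Only at smaller changes is most of it lost (56% to 13% at 0.5).

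**Conclusion.** The point holds as a lack of guaranteed error control. The correction rule has no trigger, family, divisor or alpha, and the visible text gives this trial no primary scale or week. If no correction is made, one scale over six weekly follow-ups carries a 15-21% chance of at least one p<0.05, and several scales carry more.

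This rests on alpha 0.05, n=20 in the group tested, no true change, and change-score correlation between 0.5 and 0.8. The one-scale figure does not depend on the redacted list. It should not be read as the trial's actual false-positive rate, nor as the chance of wrongly declaring CBD better than placebo. The change is worth making because it costs almost nothing and settles which result counts.

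**What to change.** Replace the Bonferroni sentence with a fixed rule:

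1. **Primary test.** The between-arm difference in BAI at week 6, two-sided alpha 0.05. The BAI already defines improvement in the open-label phase, and week 6 is the end of treatment.
2. **Secondary tests.** Between-arm differences at week 6 on a short list of named scales, with Holm's procedure across that list. Holm is never less powerful than Bonferroni.
3. **Everything else.** Other weeks, cognition and imaging reported as exploratory, with confidence intervals.

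A Bonferroni correction always applied over a listed family would also close the error-control gap. The scheme above keeps the full 5% for the main question and moves it to the randomized comparison.

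The cost is a few lines of analysis text, with no added data or visits. The downside is that intermediate weeks and unlisted scales can no longer be claimed as confirmatory.
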